2.2.5 Clinical Safety Summary

NCI Protocol #: 10220
Version Date: January 3, 2025

As of January 23, 2018, 161 patients have received Telaglenastat (CB-839) HCl as monotherapy, and 250 patients have received Telaglenastat (CB-839) HCl in combination with other agents in phase 1 and early phase 2 trials (Investigator's Brochure). Among 59 patients who received Telaglenastat (CB-839) HCl monotherapy on the TID (fasted) schedule over a dose range of 100-1000 mg, two dose limiting toxicities

(DLTs) have been observed: one at 250 mg TID (grade 3 elevated creatinine) and one at 400 mg TID (grade 3/4 elevated liver function tests (LFTs)). No DLTs have been reported on the monotherapy BID (fed state) schedule up to a dose of 800 mg. DLTs reported in combination cohorts have been: Grade 4 neutropenia (400 mg BID with 80 mg/m² IV paclitaxel weekly for three weeks in every four week cycle and 400 mg BID with 4 mg once daily (QD) pomalidomide for 21 days out of every 28 day cycle and 40 mg each week (QW) of dexamethasone), grade 3 pruritic rash (400 mg BID with 10 mg everolimus QD), grade 3 alanine aminotransferase (ALT) increase (800 mg BID with 240 mg IV nivolumab once every two weeks), and grade 4 platelet count decrease (600 mg dose with 60 mg cabozantinib QD). Although a maximum tolerated dose (MTD) has not been defined for either monotherapy or combination therapy, 800 mg BID is the highest dose that is confirmed to be safe and well tolerated in single-agent and combination Telaglenastat (CB-839) HCl studies. The 800 mg BID dose also exhibits robust exposure and pharmacodynamics effects, and has been declared recommended Phase 2 Dose (RP2D).

The largest monotherapy study of Telaglenastat (CB-839) HCl (CX-839-001) included 120 patients, 32 receiving between 100 to 800 mg of Telaglenastat (CB-839) HCl TID without food and 88 receiving between 600 to 1000 mg of Telaglenastat (CB-839) HCl with food (Investigator's Brochure). On the BID schedule, 72.7% of patients experienced an AE, the most common of which were fatigue, elevated LFTs, gastrointestinal AEs, and photophobia. These AEs were typically grade 1/2, reversible, and manageable without dose interruption or modification. Grade 3 LFTs were significantly reduced (2.3% of patients) on the BID schedule. One grade 3 AE of anemia was also considered to be related to Telaglenastat (CB-839) HCl.

As of the January 23, 2018, a total of 201 SAEs across monotherapy and combination therapy have been recorded (Investigator's Brochure). Twenty-two patients experienced at least one SAE that was considered at least possibly related to Telaglenastat (CB-839) HCl treatment. The SAEs include increased alanine aminotransferase, increased aspartate aminotransferase, anaemia, increased blood creatinine, death, dyspnoea, hepatitis, hyperglycaemia, hypertension, hypotension, hypoxia, meningitis aseptic, myositis, nausea, pyrexia seizure, stomatitis, tachycardia, and vomiting.

2.2.6 Clinical Efficacy Summary

Patients with multiple tumor types have been included in studies with Telaglenastat (CB-839) HCl as a monotherapy or in combination with other agents. As of January 23, 2018, 74 patients receiving the BID monotherapy regimen (of 88 enrolled) were RECIST evaluable for tumor response.

Best overall response of SD or better has been observed in 46% (34 patients) in a variety of malignancies, including renal cell carcinoma (RCC), triple-negative breast cancer (TNBC), non-small cell lung cancer (NSCLC), and a variety of tumors with TCA-cycle alterations. Of the 27 evaluable RCC patients, thirteen (48%) had a BOR of SD or better, including one patient with durable (1 year) PR.

2.3 Rationale

There is an unmet therapeutic need for advanced-stage cancer patients with *NF1* mutant malignant peripheral nerve sheath tumor (MPNST), *NF1* mutant cancers, *KEAP1/NRF2* & *STK11/LKB1* pathway aberrant tumors. To fill the therapeutic needs, we propose a basket clinical trial with Telaglenastat (CB-839) HCl (NSC# 795998), a potent and selective reversible inhibitor of glutaminase-1 activity. It follows that the new experimental therapeutic agent Telaglenastat (CB-839) HCl acts as an allosteric and noncompetitive inhibitor of both splice variants of the broadly expressed glutaminase-1 (gene symbol: GLS, selectivity $\sim 0.028 \mu\text{M} \pm 0.007$), but does not inhibit glutaminase-2 (GLS2, selectivity $>1000 \mu\text{M}$), which is the variant predominantly found in the human liver. Telaglenastat (CB-839) HCl has antineoplastic and has pro-apoptotic activity in a variety of human tumor cell lines, including triple-negative breast cancer (TNBC), clear cell renal cell carcinoma (RCC), and mesothelioma, as well as hematological cell lines of relapsed or refractory leukemia, multiple myeloma (MM) and non-Hodgkin's lymphoma (NHL). Among 24 non-small cell lung cancer cell lines, 11 (46%) of 24 cell lines showed substantial and significant 72-hour $1 \mu\text{M}$ Telaglenastat (CB-839) HCl monotherapy cytotoxicity. Unpublished phase 1 studies of orally-administered Telaglenastat (CB-839) HCl monotherapy have found so far that the agent is well tolerated, has no maximum tolerated dose (MTD) identified, and has a 600 mg twice daily (BID) with food for a recommended Phase II dose. Known pharmacology data are presented in Table 1. Pharmacodynamic studies in the phase 1 trials show an up to 96% reduction in patient tumor glutaminase-1 activity after a 21-day Telaglenastat (CB-839) HCl drug exposure(18). Telaglenastat (CB-839) HCl monotherapy provides minimal (<5%) clinical activity in phase I trials. As such, investigators and Calithera Biosciences, Inc. seek Telaglenastat (CB-839) HCl-agent trials with NCI CTEP. In prior work, Calithera Biosciences, Inc. has determined tumor GLS activity and blood or tumor levels of glutamine, glutamate, and aspartate after Telaglenastat (CB-839) HCl drug exposure. Inhibition of GLS activity in tumor confirms desired pharmacodynamic effect of Telaglenastat (CB-839) HCl (Fig. 2). Tandem mass spectroscopy studies of tumor or of blood samples have shown (a) desired rise in glutamine levels after Telaglenastat (CB-839) HCl, (b) fall in glutamate levels after Telaglenastat (CB-839) HCl, and (c) fall in Krebs cycle downstream aspartate levels.

Table 1. Average \pm SD of Telaglenastat (CB-839) HCl pharmacokinetic variables

Telaglenastat (CB-839) HCl	N	AUC ^{0-8h} (h*mg/L)	Cmax ($\mu\text{g}/\text{mL}$)	Cmax/dose ($\mu\text{g}/\text{L}/\text{mg}$)	Tmax (h)	Half-life (h)
600 mg BID	48	7.9 ± 5.8	1.6 ± 1.1	1.3 ± 0.9	4.2 ± 2.5	$4 \pm \text{NC}$
800-1000 mg BID	5	5.0 ± 4.7	1.0 ± 0.8	0.5 ± 0.4	2.8 ± 2.7	$4 \pm \text{NC}$

Abbreviations: N = number of patients; AUC = area under the curve; Cmax = maximum plasma concentration, Tmax = time to reach maximum plasma concentration; SD = standard deviation; h = hour; BID = twice daily by mouth; NC = not captured

Molecular Weight of Telaglenastat (CB-839) HCl: 571.579 g/mol

2.3.1 Preclinical data with Telaglenastat (CB-839) HCl (NSC# 795998)

NF1 mutation and NF1 mutant MPNST

Neurofibromatosis type 1 (NF1) is an autosomal dominant genetic syndrome caused by a mutation in or deletion of the NF1 gene. Mutations in the NF1 gene lead to the production of a nonfunctional version of neurofibromin that cannot regulate cell growth and division. As a result, tumors such as neurofibromas can form along nerves throughout the body. The NF1 phenotype is highly penetrant and occurs in 1 in 3,000 to 4,000 people worldwide. Individuals with an altered NF1 gene are at an increased risk of developing benign and/or malignant tumors. NF1 has been shown to negatively regulate Ras activity. Ras-driven cancer cells have also been known to alter glucose and glutamine metabolism. In a pre-clinical trial the role played by NF1 status in determining the sensitivity of sarcoma and melanoma cell lines to glutaminase inhibition and its effect on Ras activity was evaluated(19). A panel of soft tissue sarcoma and melanoma cell lines that were either wild-type, null or mutant for NF1 were tested. Results from in vitro proliferation assay showed that compared to wild-type NF1 (STS26T, LS141) cell lines, NF1 mutant (MPNST) and NF1 null (ST88 and MeWo) cell lines showed greater sensitivity to inhibition of proliferation by glutaminase inhibitors Telaglenastat (CB-839) HCl and BPTES. Western blot analysis showed induction of apoptosis and down regulation of mTORC1 targets such as phospho-S6K and phospho-S6 by glutaminase inhibitors only in NF1 null and NF1 mutant but not wild-type NF1 cell lines. Gene silencing experiments showed that siRNA mediated knockdown of NF1 sensitizes LS141 and STS26T cell lines to glutaminase inhibition (*Oncotarget in press*).

Conversely, overexpression of wild-type NF1 GRD (GAP related domain) in MeWo cell line resulted in decreased sensitivity to glutaminase inhibition when tested in a cell proliferation assay, thus, confirming the role played by NF1 (Fig 1). Previous reports have shown that mutation or deletion of NF1 results in activation of Ras. In order to test the effect of glutaminase inhibition on Ras activity, Ras-GTP pull down assay following the treatment with glutaminase inhibitors in NF1 null and wild-type NF1 cell lines was carried out. The results showed that glutaminase inhibition leads to down regulation of activated RAS in NF1 null but not wild-type NF1 cells. SiRNA mediated knockdown of NF1 followed by glutaminase inhibition in wild-type NF1 cell line (LS141) resulted in decreased Ras activity, further confirming the hypothesis. Results from patient derived MPNST tumor xenograft model showed a significant suppression of tumor volume when tumors were treated with glutaminase inhibitor compared to vehicle control (Fig. 2). **Taken together, the data strongly indicates that NF1 status determines the sensitivity of sarcoma and melanoma cell lines to glutaminase inhibition.** Further research is warranted to explore glutaminase inhibition as potential therapy for patients with NF1 loss and/or mutation.

[figure not shown]

Fig. 1

[figure not shown]
KEAP1/NRF2 pathway mutations are associated with greater sensitivity to GLS inhibition

Treating KRAS-mutant lung adenocarcinoma (LUAD) remains a major challenge in cancer treatment given the difficulties associated with directly inhibiting the KRAS oncoprotein. One approach to addressing this challenge is to define mutations that frequently co-occur with those in KRAS, which themselves may lead to therapeutic vulnerabilities in tumors(20).

Approximately 20% of KRAS-mutant LUAD tumors carry loss-of-function mutations in the *KEAP1* gene encoding Kelch-like ECH-associated protein 1, a negative regulator of nuclear factor erythroid 2-like 2 (NFE2L2; hereafter

NRF2), which is the master transcriptional regulator of the endogenous antioxidant response. The high frequency of mutations in *KEAP1* suggests an important role for the oxidative stress response in lung tumorigenesis. Using a CRISPR-Cas9-based approach in a mouse model of KRAS-driven LUAD, the effects of Keap1 loss in lung cancer progression were examined. It has been shown that loss of Keap1 hyperactivates NRF2 and promotes KRAS-driven LUAD in mice. Through a combination of CRISPR-Cas9-based genetic screening and metabolomic analyses, it was shown that Keap1- or Nrf2-mutant cancers are dependent on increased glutaminolysis, and this property can be therapeutically exploited through the pharmacological inhibition of glutaminase by CB-839(20). (Fig. 3) ***This provides a rationale for stratification of human patients with lung cancer harboring KRAS/KEAP1- or KRAS/NRF2-mutant lung tumors as likely to respond to glutaminase inhibition.***

Figure 3: Keap1-mutant cells display a robust sensitivity to glutaminase inhibition (Nature Medicine)(20)

[figure not shown]
STK11/ LKB1 aberrations: An integrative analysis of genomic, transcriptomic and proteomic data from early-stage and chemo-refractory LUAC and identified three robust subsets of *KRAS*-mutant LUAC dominated, respectively, by co-occurring genetic events in *STK11/LKB1* (the KL subgroup)(21). KL tumors had high rates of *KEAP1* mutational inactivation and expressed lower levels of immune markers, including PD-L1, while NRF2 is upregulated in LKB1 deficient cells(21). Hence Tumors with *STK11/ LKB1* aberrations should also be considered for potential

*NCI Protocol #: 10220
Version Date: January 3, 2025
subgroup for GLS studies (pers)*

[figure not shown]
TCGA data: Analysis of the TCGA data shows that NF1 aberrations, KEAP1/NRF2 & STK11/LKB1 pathway aberrant tumors are seen across tumor types (Figure 4 A,B and C).

Figure 4 A, B and C

[figure not shown]
Frequency of NF1 aberrations in human neoplasms

Frequency of KEAP1 aberrations in human neoplasms

Frequency of STK11 aberrations in human neoplasms

Given their distribution in multiple tumor types and strong rationale of pre-clinical sensitivity to glutaminase inhibition we propose a basket trial ([BeGIN – Basket trial of Glutaminase inhibition](#)) with single agent Telaglenastat (CB-839) HCl in pts with *NF1* mutant Malignant peripheral nerve sheath tumor (MPNST), *NF1* mutant other cancers, KEAP1/NRF2 & STK11/LKB1 pathway aberrant tumors.

2.4 Correlative Studies Background

2.4.1 Positron Emission Response Criteria in Solid Tumors (PERCIST) 1.0 Criteria for the assessment of Tumour Response to Treatment

¹⁸Fluorodeoxyglucose (¹⁸F-FDG) PET is especially valuable in assessing activity of anticancer therapies that stabilize disease rather than shrink tumors (cytostatic vs. cytoidal), and has been demonstrated to be important in assessing response to treatment in some specific tumors (e.g., gastrointestinal solid tumors)(22, 23). Since Telaglenastat (CB-839) HCl targets the metabolic pathway we hypothesize that (¹⁸F-FDG) PET may be useful in evaluating metabolic response.

Reduced metabolic activity has been shown to indicate response to treatment and/or improved survival in patients with multiple cancers(24). Some tumors may be more suitable for assessment of response to treatment by metabolic activity than by anatomic measurements, especially those with bone metastases or with RECIST non-measurable disease(25). Moreover, FDG PET can provide more rapid response data than anatomical-based measurements(26, 27).

Principles of assessing tumor response by PERCIST are similar to RECIST in many aspects, except response is evaluated by metabolic rather than anatomical criteria:

- single target lesion assessed as primary response classifier between consecutive scans
- up to 5 target lesions for each scan (maximum of 2 per organ) provide secondary response classifier data
- metabolic response criteria defined for complete response, partial response, stable disease and progressive disease

2.4.2 PET Response Criteria

As the PERCIST criteria have yet to be validated as a response classification for solid tumors, a simplified PET Response Criteria has been proposed as an exploratory objective for the current study.

A primary target lesion and up to 4 other target lesions will be identified at baseline. These target lesions should be followed consistently at each tumor assessment. Lesions should be identified as per the RECIST criteria, as described below:

- Maximum of 2 target lesions per organ, and up to 5 target lesions in total, representative of all involved organs
- Lesions selected on basis of their avidity and reproducibility across assessments

As a guide, to be considered “avid” and evaluable for these criteria, the SUVmax-BW (SUVmax normalized to actual body weight) must be $>$ SUVmax background liver normalized to actual body weight, i.e., SUVmax-BW(liver).

The following data should be captured for each lesion.

- PET scan date
- Lesion location (general anatomical location from “drop-down” menu)
- Longest diameter if applicable (mm)
- Standardized Uptake Value maximum normalized to body weight (SUVmax-BW) defined as the maximum value of SUV observed within each target lesion’s region of interest (ROI) normalized to actual body weight

Note: ROI is defined as maximum voxel within a 1.2 cm diameter (1 cm³) centered around the hottest/most avid part of the tumor.

Additionally:

- Actual body weight (BW)
- Standardized Uptake Value maximum normalized to body weight for the Liver (SUVmax-BW(liver)) defined as the maximum value of SUV observed in the background liver normalized to actual body weight.

Response should be determined as described in the table below:

PET Response Criteria Based on SUVmax-BW

Response Category	Criteria based on SUV of the most avid	Criteria based on SUV from up to 5 target
Complete Metabolic Response	Normalization of the most avid target lesion’s SUVmax-BW to SUVmax- BW(liver)	Normalization of all lesions’ (target and non-target) SUVmax-BW to SUVmax- BW(liver)

Partial Metabolic Response	$\geq 50\%$ decrease from baseline in SUVmax-BW in most avid target lesion relative to SUVmax-BW(liver)	$\geq 50\%$ decrease from baseline in sum of SUVmax-BW of all target lesions relative to SUVmax-BW(liver)
Progressive Metabolic Disease	$\geq 50\%$ increase from baseline in SUVmax-BW in most avid target lesion relative to SUVmax-BW(liver)	$\geq 50\%$ increase from baseline in sum of SUVmax-BW of all target lesions relative to SUVmax-BW(liver)
	New (evaluable) lesions	New (evaluable) lesions
Stable Metabolic Disease	Does not meet other criteria	Does not meet other criteria

2.4.3 cfDNA and analysis by next generation sequencing (NGS)

Because it has been observed that intra-tumoral genetic heterogeneity is a major contributor to therapeutic failure across different tumor types an exploratory analysis will be performed to assess the concordance of the mutational status of plasma cell-free circulating tumor DNA and tumor tissue.

Next generation sequencing will be used in this study to more comprehensively identify mutations in cell-free circulating tumor DNA. Concordance of mutational status between cell-free circulating tumor DNA and tumor tissue in solid tumor patients will be assessed both before and after study drug administration. It is anticipated that the mutations identified in cell-free circulating tumor DNA and tissue samples obtained at the same timepoints will provide a better understanding of the capabilities of the assay platforms, as well as reconcile the longitudinal changes of genomic information from different sample sources within an individual patient.

These data will be used to explore whether cell-free circulating tumor DNA can be used for precision medicine-based patient selection, as well as identify mutations that may be unresponsive to Telaglenastat (CB-839) HCl.

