1.2 Secondary Objectives

- 1.2.1 To determine the safety, PFS, TTP and OS.
- 1.2.2 To determine the ORR (highest objective response achieved between start of therapy and progression), TTR and CBR of Telaglenastat (CB-839) HCl
- 1.2.3 Correlative Objectives: To assess pharmacodynamic changes and adaptive responses and correlate with response to treatment as well as disease progression

1.3 Exploratory objectives:

- 1.3.1 Correlate ¹⁸F-FDG PET/CT pre-therapy and 8-weeks post-therapy response to Telaglenastat (CB-839) HCl therapy
- 1.3.2 Evaluate changes in level of circulating tumor DNA at baseline, one month on-treatment and time of progression (MoCHA Labs) to treatment response.
- 1.3.3 Quantify the peripheral blood concentrations of the metabolites: Aspartate, Glutamate, Glutamine and Arginine (@Mayo clinic Oncometabolomics core) and correlate with response.
- 1.3.4 Evaluate the PD effect of Telaglenastat (CB-839) HCl on systemic levels of the TCA cycle metabolites in peripheral blood (baseline and one month) as part of the protocol.
- 1.3.5 Evaluate tumor by Reverse phase protein array (@core facility at MD Anderson) and RNA seq to evaluate changes from pre-treatment, during treatment and post treatment specimens.
- 1.3.6 Perform PDX modelling-co-clinical trials (@[name] lab MD Anderson) to understand response / resistance mechanisms and also evaluate combination therapies for future development.

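### In the most-avid-lesion column of the PET criteria (2.4.2), the cut-off for entry and for Complete Metabolic Response is the same liver value with no minimum change, so 'complete' can need a smaller fall than 'partial' and can arise from scan noise in lesions near liver level

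*Combined protocol and SAP*

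**What the plan says.** Objective 1.3.1 is to correlate "PET/CT pre-therapy and 8-weeks post-therapy response to Telaglenastat (CB-839) HCl therapy". Section 2.4.2 supplies the classification: because PERCIST is not yet validated, "a simplified PET Response Criteria has been proposed as an exploratory objective for the current study".

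The parts of 2.4.2 that matter are these.

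- **Entry.** "As a guide, to be considered “avid” and evaluable for these criteria, the SUVmax-BW (SUVmax normalized to actual body weight) must be" greater than "SUVmax background liver normalized to actual body weight, i.e., SUVmax-BW(liver". The liver reference is itself a maximum, "defined as the maximum value of SUV observed in the background liver normalized to actual body weight".
- **Complete Metabolic Response, most avid lesion.** "Normalization of the most avid target lesion’s SUVmax-BW to SUVmax- BW(liver".
- **Complete Metabolic Response, up to five target lesions.** "Normalization of all lesions’ (target and non-target) SUVmax-BW to SUVmax- BW(liver".
- **Partial Metabolic Response (PMR), most avid lesion.** At least a 50% "decrease from baseline in SUVmax-BW in most avid target lesion relative to SUVmax-BW(liver". The multi-lesion column applies the same percentage to the sum over target lesions.
- **Progressive and stable.** Progression is a rise of at least 50% relative to liver, or a new evaluable lesion. Stable is everything else.

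The section gives no margin above liver for entry, no minimum fall for CMR, no repeat PET and no allowance for repeatability. It does not define 'relative to' liver. Section 9 contains no PET analysis, and 12.1.4.3 keeps FDG-PET response out of best overall response.

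**The concern.** The floor for entering the most-avid-lesion classification and the threshold for its best category are the same number. A hottest lesion just above liver at baseline needs only a small drop to be called complete. A very hot lesion can lose almost half its uptake relative to liver and still be called stable. A response scale should be ordered by amount of response, and on the ordinary reading of the partial criterion this one is not.

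Both the lesion and liver values are single maxima that vary from scan to scan. Near the shared cut-off, part of the CMR count can therefore be measurement error. There is no control arm to show the background rate. At stake is the exploratory association between PET change and response: false CMRs would dilute a real association and could inflate a reported metabolic complete-response rate.

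**Working it through.** **Inputs.** From 2.4.2: entry at r > 1, CMR at follow-up ratio <= 1, PMR at a fall of at least 50%, where r is the baseline ratio of lesion to liver SUVmax-BW. The plan states no sample size, error rate or repeatability for PET, so there is no figure of its own to reproduce.

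**Step 1: size of fall, reading 'relative to liver' as the ratio.** CMR needs a fall of 1 - 1/r; PMR needs 0.50. They are equal when 1 - 1/r = 0.5, so r = 2.

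| r | Fall for CMR | Fall for PMR |
|---|---|---|
| 1.1 | 9% | 50% |
| 1.2 | 17% | 50% |
| 1.5 | 33% | 50% |
| 2.0 | 50% | 50% |
| 3.0 | 67% | 50% |

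Example: 1.2 to 1.0 is a 17% fall and is complete; 8.0 to 4.1 is 1 - 4.1/8.0 = 49% and is stable. Raw SUV with an unchanged liver value gives the same table.

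**Step 2: the other reading.** If the 50% applies to the excess over liver, PMR is reached at a ratio of 1 + (r - 1)/2, a fall of (r - 1)/(2r): 4.5% at r = 1.1, 8.3% at 1.2, 16.7% at 1.5. CMR needs (r - 1)/r, exactly twice that, so the order is restored. The shared cut-off is unchanged, and CMR still needs only 9% at r = 1.1.

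**Step 3: noise alone, one lesion.** Assume no true change and a scan-to-scan change in the log ratio that is normal with mean 0 and SD d at a given observed baseline. Then P(CMR) = Phi(-ln r / d). The range for d is an assumption. For orientation, independent errors with CV 10% for lesion and none for liver give d = 0.141; CV 15% for both gives d = 0.298.

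| d | r = 1.1 | r = 1.2 | r = 1.3 | r = 1.5 | Chance 50% fall in ratio |
|---|---|---|---|---|---|
| 0.05 | 2.8% | 0.0% | 0.0% | 0.0% | 0.0% |
| 0.10 | 17.0% | 3.4% | 0.4% | 0.0% | 0.0% |
| 0.15 | 26.3% | 11.2% | 4.0% | 0.3% | 0.0% |
| 0.20 | 31.7% | 18.1% | 9.5% | 2.1% | 0.03% |
| 0.25 | 35.2% | 23.3% | 14.7% | 5.2% | 0.3% |
| 0.30 | 37.5% | 27.2% | 19.1% | 8.8% | 1.0% |

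**Step 4: multi-lesion column.** All lesions must normalize. With k lesions all at r = 1.1 and independent errors, the probability is the single-lesion value to the power k. At d = 0.10: 17.0% for one, 2.9% for two, 0.01% for five. At d = 0.20: 31.7%, 10.0%, 0.3%.

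**Step 5: over all evaluable patients, single lesion, no drug effect.** This needs an assumed avidity distribution as well. With a lognormal true ratio (geometric SD 1.6 or 2.0), lesion CV 10-15% and liver CV 0-15%, simulation gives a CMR rate of 3.8-8.7% for a median ratio of 1.5, 1.8-5.0% for 2, 0.3-2.2% for 3 and 0.1-1.1% for 4.

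**The case against.** The strongest reply is that little rests on this table. The criteria are exploratory, PET stays out of best overall response, and Section 9 ties no analysis to the categories. Objective 1.3.1 names no category, and per-lesion SUVmax-BW is recorded, so a continuous analysis is already possible. All of this stands and limits the point to a minor one.

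The protections inside 2.4.2 are also real. The avidity rule is only a guide, lesions are chosen for avidity and reproducibility, the hottest lesion is the least likely to sit near liver, and the other column requires every lesion to normalize. They reduce the problem without removing it: none sets a numerical margin, and the most-avid-lesion column has no all-lesions rule.

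The inversion depends on wording that 2.4.2 leaves open, as Step 2 shows. The noise figures rest on an assumed SD. Error shared by lesion and liver within a scan would cancel in the ratio, which favours the lower part of the range.

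Stronger readings are tempting and not supported:

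- **That scan noise does create complete responders in this trial.** The documents give neither repeatability nor avidity, so 'can' is as far as they go.
- **That partial response is unreachable below twice liver.** This holds for the single lesion only. In the multi-lesion column, two targets at 1.8 falling to 0.6 and 1.1 give 1 - 1.7/3.6 = 53% without full normalization, which is partial.
- **That the most avid lesion is the trial's designated primary PET classifier.** Section 2.4.1 lists a single target lesion among PERCIST principles; 2.4.2 does not say which of its two columns governs.
- **That false CMRs would pass as proof of drug activity.** Activity is judged by RECIST.

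**Conclusion.** The point holds for the most-avid-lesion column. The shared cut-off with no minimum change is plain in the text and needs no assumption. On the ratio or raw-SUV reading, every hottest lesion starting below twice liver reaches complete with a smaller fall than partial requires. On the excess-over-liver reading that inversion goes, but the shared cut-off stays.

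The noise effect is conditional on the assumed d of 0.05-0.30. It can be material for hottest lesions within about 1.2-1.3 times liver and is small from about r = 1.5 unless d is near 0.30. It is much smaller when several lesions must all normalize. The trial-wide effect depends on how avid the enrolled tumours are, which the documents do not say.

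The consequence is confined to exploratory objective 1.3.1. The primary endpoint and the two-stage decision rule are untouched, so this is a worthwhile improvement rather than a necessary correction.

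**What to change.** 1. In 2.4.2, state that 'relative to liver' means the ratio of lesion to liver SUVmax-BW.
2. For objective 1.3.1, make the continuous percent change in that ratio the main PET measure correlated with response, in all patients with paired PET scans.
3. Report the metabolic response categories as descriptive. Flag every CMR with less than a 50% fall in the ratio (possible only when the baseline is below twice liver), and give the CMR rate with and without the flagged cases.

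A stand-alone 50% condition for CMR, or an entry floor at twice liver, is not needed. The first would leave a lesion going from 1.2 to 0.65 times liver (a 46% fall, ending below liver) as stable; the second would remove patients from a categorical analysis that may already be small.

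The cost is wording and a little extra analysis. Lesion and liver values are already captured, no scan is added and no patient is dropped. The headline metabolic complete-response rate may be lower once the flagged cases are set aside.
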